5.4.1.4. Childhood Health Assessment Questionnaire (CHAQ)

The functional status of subjects will be assessed by the CHAQ. Parents are to complete this questionnaire to assess the degree of difficulty the subject has in accomplishing tasks in 8 functional areas (dressing and grooming, arising, eating, walking, hygiene, reaching, gripping, and activities of daily living). Responses in each functional area are scored as 0 = without difficulty, 1 = with some difficulty, 2 = with much difficulty, 3 = unable to do, or 4 = not applicable response options. If aids or devices are used or assistance is required, the minimal score for the corresponding area is 2. The CHAQ has been shown to be responsive to disease change. A decrease of 0.188 has been determined to be a meaningful clinical improvement.

The disability index is calculated as the mean of the 8 domains and yields a score between 0 (no disability) and 3 (most severe disability). The disability index is not computed if the subject does not have scores for at least 6 categories.

5.4.1.5. Juvenile Arthritis Disease Activity Score (JADAS)

The JADAS (modified for using CRP) is computed by assessing the following variables:

- (1) Physician global rating of overall disease activity, measured on a 100-mm horizontal VAS (0 no activity; 100 maximum activity);
- (2) Parent/child ratings of well-being and pain, assessed on a 100-mm Horizontal Line Visual Analog Scales,³
- (3) Number of active joints, assessed in 71, 27, or 10 joints (JADAS 71, JADAS 27, and JADAS 10, respectively); and
- (4) CRP was truncated to a 0-10 scale according to the following formula: ((CRP [mg/L]-10)/10), similar to the truncated ESR used in JADAS-ESR. Before calculation, CRP values <10 mg/L are converted to 10 and CRP values >110 mg/L are converted to 110.⁵

JADAS-71 includes the entire number of joints. The JADAS-27 includes the following joints: cervical spine, elbows, wrists, meta-carpophalangeal joints (from first to third), proximal interphalangeal joints, hips, knees, and ankles. JADAS-10 is based on the count of any active joint, irrespective of its type, up to a maximum of 10 joints.

The JADAS is calculated as the sum of the scores of its 4 components, which yields a global score of 0–101, 0–57, and 0–40 for the JADAS 71, JADAS 27, and JADAS 10, respectively.

JADAS 10, 27, and 71 minimal disease activity^{2,5} is defined as the presence of all of the following:

- (1) Physician's global assessment of disease activity of \leq 3.5,
- (2) Parent's global rating of well-being of ≤ 2.5 , and
- (3) Swollen joint count of ≤ 1 in patients with polyarthritis.

JADAS inactive disease is defined as a total JADAS score of ≤ 1 .

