5.4.1.2. Inactive Disease

Inactive disease is indicated by the presence of all of the following:

- 1. No joints with active arthritis
- 2. No fever, rash, serositis, splenomegaly, hepatomegaly or generalized lymphadenopathy attributable to JIA
- 3. No active uveitis
- 4. Normal CRP ($\leq 0.287 \text{ mg/dL}$ for subjects without underlying inflammatory disease)
- 5. Physician Global Assessment of disease activity indicating no active disease (≤5 mm VAS)
- 6. Duration of morning stiffness <15 minutes

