5.4.2. Analysis Methods

Unless otherwise specified, the analysis population will be the full analyses set defined in Section 2.3.2.

Summaries over time will be for all visits data was collected through Week 28, 52, and 252, if the visit of the endpoint is not specified. Simple descriptive summary statistics, such as n, mean, SD, median, IQ range, minimum, and maximum for continuous variables, and counts and percentages for discrete variables will be used to summarize most data.

The following endpoints will be summarized over time.

- 1. The proportion of subjects who are JIA ACR 30, 50, 70, and 90 responders
- 2. The proportion of subjects who have inactive disease
- 3. The proportion of subjects in clinical remission on medication for pJIA
- 4. The improvement from baseline in the JIA ACR core set of components
- 5. The proportions of subjects who are JIA ACR 30, 50, 70, and 90 responders by disease subtype, and/or age through Week 52
- 6. The change from baseline in CHAQ
- 7. CRP concentrations
- 8. The change from baseline in JADAS 10, 27, and 71 scores
- 9. The proportion of subjects who achieve JADAS 10, 27, and 71 minimal disease activity

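### JADAS is defined as a sum of unconverted 100-mm scales, which contradicts its stated ranges, and the parent component and the minimal-disease-activity units are not defined

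*SAP*

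**What the plan says.** SAP 5.4.1.5 lists four JADAS components:

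- the physician rating: "Physician global rating of overall disease activity, measured on a 100-mm horizontal VAS (0 no activity; 100 maximum activity");
- the parent component: "Parent/child ratings of well-being and pain, assessed on a 100-mm Horizontal Line Visual Analog Scales";
- the number of active joints, counted to 71, 27 or 10;
- CRP, the only component given a conversion: "CRP was truncated to a 0-10 scale according to the following formula".

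It then says "The JADAS is calculated as the sum of the scores of its 4 components, which yields a global score of" 0-101, 0-57 and 0-40 for JADAS 71, 27 and 10. Minimal disease activity requires a physician global of 3.5 or less, "Parent's global rating of well-being of" 2.5 or less, and at most one swollen joint. Neither VAS cut-off has a unit.

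Protocol 9.2.1.6 also has 100-mm scales, the same ranges and the same unitless cut-offs, so it does not settle the matter. Protocol 9.2.1.4 collects pain and overall well-being as two separate 0-100 mm items. SAP 5.4.2 lists both "The change from baseline in JADAS 10, 27, and 71 scores" and "The proportion of subjects who achieve JADAS 10, 27, and 71 minimal disease activity" for summary over time.

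**The concern.** The summation rule and the ranges cannot both be right. Two 0-100 components cannot fit inside a total of 40, 57 or 101. If the rule were programmed as written, change from baseline in all three JADAS versions would be mis-scored, and the two VAS components would dominate the joint count and CRP.

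Two further gaps would remain after the scale was corrected. The parent component names two ratings but gives no rule for turning them into one value. And every VAS in the study is recorded in mm, so a programmer could apply 3.5 and 2.5 directly to the mm values. Those cut-offs do not enter the JADAS sum, so the stated ranges would not expose that mistake. Stricter cut-offs can only remove subjects from the minimal-disease-activity group, so any resulting bias in that proportion is downward.

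**Working it through.** **Inputs (SAP 5.4.1.5).** Joint maximum 71, 27 or 10. CRP is truncated to 10-110 mg/L, so its term runs from (10 - 10)/10 = 0 to (110 - 10)/10 = 10. Physician VAS 0-100 mm. Parent VAS 0-100 mm. Stated maxima 101, 57 and 40.

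**Formula.** Maximum = physician + parent + joints + CRP.

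| VAS scale | Parent component | JADAS 71 | JADAS 27 | JADAS 10 | Matches the SAP? |
|---|---|---|---|---|---|
| mm, as written | one value | 100+100+71+10 = 281 | 100+100+27+10 = 237 | 100+100+10+10 = 220 | no |
| mm, as written | well-being + pain | 381 | 337 | 320 | no |
| divided by 10 | well-being + pain | 10+20+71+10 = 111 | 67 | 50 | no |
| divided by 10 | one value, or the mean of two | 10+10+71+10 = 101 | 10+10+27+10 = 57 | 10+10+10+10 = 40 | yes, all three |

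The joint count is not the source of the mismatch. The JADAS 27 list totals 1+2+2+6+10+2+2+2 = 27, assuming bilateral joints and ten proximal interphalangeal joints.

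**Weight of the VAS components (share of the maximum), for JADAS 71, 27 and 10.**
- On 0-10 scales: 20/101 = 19.8%, 20/57 = 35.1%, 20/40 = 50.0%.
- As written, with one parent value: 200/281 = 71.2%, 200/237 = 84.4%, 200/220 = 90.9%.

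**Parent component after rescaling.** The ranges exclude adding well-being and pain, but well-being alone, pain alone and their mean all fit. The largest possible differences, reached when one item is 0 mm and the other 100 mm, are:
- well-being versus pain: 10 points, or 10/101 = 9.9%, 10/57 = 17.5% and 10/40 = 25.0% of the range;
- either one versus the mean: 5 points, or 5.0%, 8.8% and 12.5%.

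**Illustration with assumed values.** Take physician 40 mm, well-being 20 mm, pain 60 mm, 8 active joints and CRP 15 mg/L, so the CRP term is (15 - 10)/10 = 0.5. JADAS 10 is then:

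| Parent value | 0-10 scales | Raw mm |
|---|---|---|
| well-being | 4+2+8+0.5 = 14.5 | 40+20+8+0.5 = 68.5 |
| pain | 4+6+8+0.5 = 18.5 | 40+60+8+0.5 = 108.5 |
| mean | 4+4+8+0.5 = 16.5 | 40+40+8+0.5 = 88.5 |

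Every raw-mm score exceeds the stated maximum of 40.

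**Cut-off units.** On a 0-10 scale the cut-offs equal 3.5 x 10 = 35 mm and 2.5 x 10 = 25 mm. SAP 5.4.1.2 sets the inactive-disease limit with its unit: "Physician Global Assessment of disease activity indicating no active disease (≤5 mm VAS"). Read in mm, minimal disease activity (3.5 mm) would demand a lower physician score than inactive disease (5 mm), which makes no sense. Read as 35 mm, the two definitions are in the right order.

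**Supporting history.** The protocol's amendment log shows that superseded JADAS text had the same ranges and cut-offs on a 10-cm scale. This supports the 0-10 reading; the contradiction itself rests on current text.

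**The case against.** The strongest reply is that the section settles its own scale. With 71, 27 or 10 for joints and 10 for CRP, the stated ranges leave exactly 20 points for the two VAS components, so dividing by 10 is the only admissible conversion. Raw-mm scores would be conspicuously out of range and soon caught. The mm reading of the cut-offs is incoherent against the inactive-disease limit, so context resolves that too. The text names well-being and pain together, which favours their mean over either alone; the 10-point figure compares two readings that the wording supports less well, and only at the extremes. Finally, these are descriptive endpoints with no testing (SAP 5.1.1).

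Much of this stands. The intended scale can be inferred, the raw-mm maxima show what literal programming would do rather than what is planned, and 5 points is the bound if the mean is taken as the reference. But the SAP writes out the conversion for CRP and omits it for the two components that need it most. The mean is nowhere stated. A wrong unit on the cut-offs would not breach any stated range. Being able to infer a likely intention is not the same as having a definition from which the results can be reproduced.

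**Conclusion.** The concern holds, and the definition is wrong as written. Followed literally with one parent value, it gives maxima of 281, 237 and 220 against the stated 101, 57 and 40. Only 0-10 scaling with a single 0-10 parent value reproduces the stated ranges. After that correction, the undefined parent component still leaves a possible difference of up to 10 points between well-being and pain, or up to 5 points between either and their mean.

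The reach is limited to change in JADAS and the minimal-disease-activity proportion. The JADAS inactive-disease cut-off (total of 1 or less) also depends on the scale but is not among the endpoints listed in SAP 5.4.2. The PK primary endpoints, the sample size and the JIA ACR 30 discontinuation rule do not use JADAS. The documents do not show what was programmed, and the actual bias cannot be calculated from them. Raw data are unaffected, so scores can be re-derived. It should be fixed, but it does not threaten the study's main conclusions.

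**What to change.** In SAP 5.4.1.5:

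1. State that each VAS in mm is divided by 10 before summing.
2. State how the single 0-10 parent component is formed: well-being, pain or their mean.
3. Give the unit of the 3.5 and 2.5 cut-offs. On the 0-10 scale they equal 35 mm and 25 mm; the sponsor should confirm this against the instrument's definition.
4. Add a programming check that no score exceeds 101, 57 or 40. This check cannot test the cut-off units, so item 3 is needed as well.

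If JADAS outputs already exist, check the derivation program against these statements and re-derive where it differs.

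The cost is SAP wording and derived-variable programming, with no new data. Protocol section 11 leaves specific details to the SAP, so no protocol amendment is needed for this alone. Protocol 9.2.1.6 can be aligned at the next amendment, if there is one.

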5.4.2. Analysis Methods

Unless otherwise specified, the analysis population will be the full analyses set defined in Section 2.3.2.

Summaries over time will be for all visits data was collected through Week 28, 52, and 252, if the visit of the endpoint is not specified. Simple descriptive summary statistics, such as n, mean, SD, median, IQ range, minimum, and maximum for continuous variables, and counts and percentages for discrete variables will be used to summarize most data.

The following endpoints will be summarized over time.

- 1. The proportion of subjects who are JIA ACR 30, 50, 70, and 90 responders
- 2. The proportion of subjects who have inactive disease
- 3. The proportion of subjects in clinical remission on medication for pJIA
- 4. The improvement from baseline in the JIA ACR core set of components
- 5. The proportions of subjects who are JIA ACR 30, 50, 70, and 90 responders by disease subtype, and/or age through Week 52
- 6. The change from baseline in CHAQ
- 7. CRP concentrations
- 8. The change from baseline in JADAS 10, 27, and 71 scores
- 9. The proportion of subjects who achieve JADAS 10, 27, and 71 minimal disease activity

6. SAFETY

Safety will be assessed by summarizing the occurrences and type of AEs, and examining the changes in the laboratory parameters.

Subjects who received at least 1 IV study agent administration will be included in the analysis (full analysis set).

6.1. Safety Table(s) Presentation

If a subject discontinues study participation, the follow-up time will stop at the day of study participation discontinuation.

The safety summary tables will be presented through the following periods:

- 1. Through Week 28
- 2. Through Week 52
- 3. Through Week 252

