Infusion Reaction Evaluations

Before an infusion is started, the appropriate personnel, medications (eg, epinephrine, inhaled beta agonists, antihistamines and corticosteroids), and other requirements to treat anaphylaxis should be available. The subject may be premedicated with prophylactic drugs (eg, diphenhydramine) prior to starting the infusion based on investigator's discretion but this is not mandatory. However, corticosteroids for prophylaxis are not allowed. Premedications should be recorded in the eCRF.

The investigator or qualified designee will evaluate the subject for infusion reactions according to the Time and Events Schedule.

An infusion reaction is any unfavorable or unintended sign that occurs during the infusion or within 1 hour of completion of the infusion. All subjects must be carefully observed for symptoms of an infusion reaction. Through Week 52, subjects will be observed for at least 60 minutes after completion of the IV administration of study agent for symptoms of an infusion reaction. After Week 52, subjects will be observed at the discretion of the investigator after completion of the IV administration of study agent for symptoms of an infusion reaction. If an infusion reaction is observed, the subject should be treated at the investigator's discretion.

The investigator will record the infusion reaction in the AE page. If no infusion reaction is observed, the investigator will note this in the subject's medical records (source data).

Allergic Reactions

Through Week 52, all subjects must be observed carefully for symptoms of an allergic reaction (eg, urticaria, itching, hives) for at least 60 minutes after the completion of the infusion. After Week 52, subjects must be observed carefully for symptoms of an allergic reaction at the discretion of the investigator after completion of the infusion. If mild or moderate allergic reaction is observed, acetaminophen or NSAIDs and diphenhydramine at approved pediatric doses may be administered.

Subjects with severe reactions following an infusion that result in bronchospasm with wheezing and/or dyspnea and require ventilatory support, or symptomatic hypotension with a decrease in systolic blood pressure greater than 40 mm mercury (Hg), will not be permitted to receive any additional study agent infusions. In the case of such reactions, appropriate medical treatment should be administered.

Early Detection of Active Tuberculosis

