11.7. Safety Analyses

Adverse Events

The verbatim terms used in the CRF by investigators to identify adverse events will be coded using the Medical Dictionary for Regulatory Activities (MedDRA). All reported adverse events with onset during the treatment phase (ie, treatment-emergent adverse events, and adverse events that have worsened since baseline) will be included in the analysis. For each adverse event, the percentage of subjects who experience at least 1 occurrence of the given event will be summarized by treatment group.

Summaries, listings, datasets, or subject narratives may be provided, as appropriate, for those subjects who die, who discontinue treatment due to an adverse event, or who experience a severe or a serious adverse event.

The following analyses will be used to assess the safety of subjects in this trial:

- The occurrence and type of AEs
- The occurrence and type of SAEs
- The occurrence and type of reasonably related AEs
- The occurrence of infusion reactions
- The occurrence of ANA and anti-dsDNA antibodies
- The occurrence of antibodies to golimumab
- The occurrence of markedly abnormal laboratory (hematology and chemistry) parameters

Clinical Laboratory Tests

Laboratory data will be summarized by type of laboratory test. Reference ranges and markedly abnormal results (specified in the Statistical Analysis Plan) will be used in the summary of laboratory data. Changes from baseline results will be presented in pre- versus posttreatment cross-tabulations (with classes for below, within, and above normal ranges). Frequency tabulations of the abnormalities will be made. A listing of subjects with any markedly abnormal laboratory results will also be provided.

Vital Signs

Descriptive statistics of pulse/heart rate, respiratory rate, temperature, and blood pressure (systolic and diastolic) values and changes from baseline will be summarized at each scheduled time point in the Schedule of Events.

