2.3.2. Full Analysis Set

The full analysis set includes all enrolled subjects who received at least 1 infusion.

This analysis set will be used for efficacy analysis and safety analysis, unless otherwise specified.

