6.2. Adverse Events

Treatment-emergent AEs will be summarized by system organ class and preferred term defined by MedDRA.

The following treatment-emergent AE summary tables will be provided for this study:

- Any AEs
- SAEs

- AEs with severe intensity
- AEs and SAEs that are reasonably related to study agent
- AEs leading to discontinuation of study agent
- Infusion reactions
- Infections and infections requiring oral or parenteral anti-microbial treatment
- Serious infections

In addition to the summary tables, a listing of subjects who died and listings of subjects with the following AEs will be presented: SAEs, AEs leading to discontinuation of study agent(s), anaphylactic reactions or serum sickness reactions, malignancy, tuberculosis, clinically important hepatobiliary events (defined as $ALT \ge 3 \times ULN$ and either bilirubin $\ge 2 \times ULN$ or occurrence of a serious adverse event in the hepatobiliary system-organ class), and demyelination.

Infusion reactions and infection:

- An infusion reaction is identified as any unfavorable or unintended sign that occurs during the infusion or within 1 hour of completion of the infusion. Infusion reactions are captured in the eCRF.
- An infection is identified as any AE that was recorded as an infection by the investigator on the eCRF.

Since safety should be assessed relative to exposure, the following summaries will be presented:

- Proportion of subjects receiving scheduled IV study agent administrations at each study agent administration visit.
- Summary of cumulative golimumab dose.

In addition, all AE summary tables will include average weeks of follow-up and average number of IV infusions.

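### Long-term safety is reported only as cumulative percentages of all treated subjects, so extension risk cannot be read from the tables and the change in monitoring after Week 52 is hidden

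*SAP*

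**What the plan says.** SAP 6.1 states that "The safety summary tables will be presented through the following periods": through Week 28, through Week 52 and through Week 252. All three start at Week 0, and none isolates the extension.

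The measure is a subject percentage. Protocol 11.7 says that for each adverse event "the percentage of subjects who experience at least 1 occurrence of the given event will be summarized by treatment group". SAP 6.3 gives proportions of subjects by maximum CTCAE grade and with markedly abnormal results. The denominator is set in SAP 2.3.2: "The full analysis set includes all enrolled subjects who received at least 1 infusion".

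SAP 6.2 accepts that safety has to be judged against exposure. For this it offers infusions received at each visit, cumulative dose, and the rule that "all AE summary tables will include average weeks of follow-up and average number of IV infusions". It plans no event rate.

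On ascertainment, SAP 6.2 defines an infusion reaction as a sign "that occurs during the infusion or within 1 hour of completion of the infusion". Protocol 9.4 sets the matching observation: "Through Week 52, subjects will be observed for at least 60 minutes after completion of the IV administration of study agent". It continues: "After Week 52, subjects will be observed at the discretion of the investigator after completion of the IV administration of study agent". The timed vital signs change in the same way. Routine laboratory draws are at Weeks 4, 12, 20, 28, 36, 44 and 52 after baseline (Protocol Table 1), then at Weeks 100, 156, 204 and 252 (Tables 2 and 3). The protocol's amendment log shows that Amendment 4 (16 December 2019) made these extension changes and that extension draws had been every 24 weeks before it. The current SAP is dated 1 August 2018, and its Section 6.6 still lists antibody sampling every 24 weeks in the extension.

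**The concern.** The Week 252 tables will be the long-term safety statement for children on this drug. As planned, each figure merges two periods that differ in how many subjects are at risk, how long they are followed and how closely they are watched. The definition of an infusion reaction stays the same while the fixed means of detecting one is relaxed.

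A reader who wants the risk in the extension has to subtract the Week 52 count from the Week 252 count. That gives only subjects with a first event after Week 52, so repeat reactions disappear. It is also set against everyone ever treated, although entry to the extension is optional (Protocol 3.1.3). Printing average follow-up and average infusions beside a percentage does not turn it into a rate when subjects leave at different times.

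**Working it through.** **1. The plan's own figure.** Protocol Table 4 gives 17 hematology samples per subject. The schedule before Amendment 4 reproduces it: 9 draws through Week 52 (screening and Weeks 0, 4, 12, 20, 28, 36, 44, 52) plus 8 at 24-week spacing (Weeks 76 to 244) = 17. Under Amendment 4 the count is 9 + 4 = 13.

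**2. Draw density.** First year: 7 post-baseline draws in 52 weeks. Extension before Amendment 4: 8 in 200 weeks, or 8 × 52/200 = 2.08 per 52 weeks. After it: 4 × 52/200 = 1.04 per 52 weeks.

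**3. Infusions.** Weeks 0, 4, 12, 20, 28, 36, 44, 52 = 8. Weeks 60 to 244 by 8 = 24. Total 32.

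**4. Infusion reactions, illustration.** Let p be the reaction risk per infusion and d the share of reactions after Week 52 that are still captured. I take p = 0.4% from the adult IV study (Protocol 1.1.2.1, share of infusions with a reaction through Week 112), assume that it carries over and is constant, and bracket it. The documents give no value for d.

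- Subject percentage through Week 52 = 1 − (1 − p)^8
- Subject percentage through Week 252 = 1 − (1 − p)^8 × (1 − dp)^24

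| p | Week 52 | Week 252, d = 1 | d = 0.5 | d = 0 |
|---|---|---|---|---|
| 0.2% | 1.59% | 6.21% | 3.92% | 1.59% |
| 0.4% | 3.16% | 12.04% | 7.70% | 3.16% |
| 0.8% | 6.22% | 22.67% | 14.82% | 6.22% |

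The Week 252 figure never drops below the Week 52 figure. It falls short of what constant ascertainment would have shown.

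**5. With dropout.** Take 120 treated and 100 at Week 52 (the SAP 1.2 planning figures). Assume 60 to 100 complete the extension, early leavers have 4 infusions and extension leavers have 12 extension infusions. At p = 0.4% and d = 0.5 the percentage goes from 2.89% at Week 52 to between 5.93% and 6.68% at Week 252. With full capture it would be 8.85% to 10.30%.

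**6. Laboratory, illustration.** Let q be the chance that a draw shows a transient marked abnormality, with draws independent (assumed). The cumulative percentage is 1 − (1 − q)^draws. For q = 1%:

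- Week 52 (7 post-baseline draws): 6.79%
- Week 252, current schedule (11): 10.47%
- Week 252, earlier schedule (15): 13.99%

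For q = 0.5% the two Week 252 figures are 5.36% and 7.24%; for q = 2%, 19.93% and 26.14%. Against the first-year frequency the gap would be wider, since 7 × 200/52 is about 27 extension draws, not 4 or 8.

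**7. Denominator.** On the planning figures, 120/100 = 1.2. Even with perfect detection, the difference between the Week 252 and Week 52 percentages uses a denominator about 20% larger than the number who could enter the extension.

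**8. When monitoring changed.** From 28 February 2017, when the rationale in Amendment 3 reports about half the subjects enrolled, to 16 December 2019 is 1,021 days, or 145.9 weeks. That half, if still on study, had reached about Week 146 or later under the fuller schedule.

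**The case against.** The best case for the plan has four parts.

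- A subject percentage on a fixed denominator cannot decline with time. Separate Week 28 and Week 52 tables keep the intensive period visible.
- Observation did not stop. Protocol 9.4 requires careful observation of all subjects without a week limit, and Tables 2 and 3 keep infusion-reaction and adverse-event evaluation at every infusion visit. Signs during the infusion are still within the definition, and anaphylactic and serum sickness reactions are listed individually.
- The relaxation came with Amendment 4, so much of the extension was observed under the older rules.
- The study is single-arm and descriptive, so unequal exposure cannot bias a comparison between arms.

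All of this stands, and it limits the point. It rules out two stronger readings. A reader might infer that the Week 252 percentages are diluted downwards; step 4 shows that they are not. A reader might also infer that 24 of 32 infusions carry no required observation; only the fixed 60-minute minimum and the timed vital signs were removed.

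It does not answer the rest. The Week 52 table says nothing about risk in the extension, and subtraction loses repeat events and keeps the wrong denominator. The laboratory contrast was there before Amendment 4: about 2 draws a year against 7.

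**Conclusion.** The point holds in a limited form. The Week 252 tables mix two levels of ascertainment and unequal follow-up in one crude percentage. Risk among those still at risk in the extension cannot be read from them, and the SAP does not follow its own exposure principle through to a rate. Infusion reactions and transient laboratory abnormalities may be understated against the first-year standard.

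The documents do not allow the amount to be fixed. The illustrations (7.70% against 12.04% for reactions, 10.47% against 13.99% for laboratory abnormalities) rest on an adult per-infusion risk, assumed capture of one half, an assumed per-draw risk of 1%, constant risk, and Amendment 4 applying to the whole extension. Because part of the extension came before Amendment 4, the true shortfall from that change should be smaller at the same assumed values.

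A reader might form a pooled per-infusion rate from the printed averages. It would be (8 + 24d)/32 of the true rate, or 63% at d = 0.5. That dilution is real for such a rate, but the SAP does not plan one, so it is not a defect of the planned tables.

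**What to change.** - **SAP 6.1:** add the period after Week 52 through Week 252, with subjects who entered the extension as the denominator.
- **SAP 6.2, infusion reactions:** report them per infusion for each period, counting repeats. Infusions are the right unit because their frequency falls from 8 in the first 52 weeks to 24 × 52/200 = 6.24 per 52 weeks.
- **SAP 6.2, adverse events, serious adverse events and serious infections:** report events per 100 subject-years with 95% confidence intervals for each period.
- **SAP 6.3:** report markedly abnormal and CTCAE-graded results by period, with the number of draws.
- **Split:** where possible, divide extension reactions and laboratory results before and after Amendment 4 took effect, since a cut at Week 52 alone still mixes the two regimes.
- **Footnote:** state that monitoring changed with Amendment 4 and that later rates may be under-ascertained.

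The split makes the change visible but does not recover missed events. The cost is SAP wording and a few extra tables from data already collected, with no change to visits or procedures.
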